## 5.6. Imputation of Partial Dates

### Adverse Events and Concomitant Medications

- If the AE start date is completely missing, or if the subject was not treated, no imputation will be conducted.
- If the AE start date is missing day and month, do the following:
  - If the treatment start date is missing or the AE start year does not fall in the same year as that of the treatment start date or if the AE record contains information to indicate that the event ended before the treatment start date (e.g. the AE end date month and year are earlier than the treatment start date or the full AE end date is known and occurs earlier than the treatment start date), then set the AE start month and day to January 1st.
  - Otherwise, set the AE start date to the treatment start date.
- If only the AE start day is missing, do the following:
  - If the study treatment start date is missing or the AE start month and year does not fall in the same month and year as that of the treatment start date or if the AE

Sponsor: Aduro Biotech, Inc.  
Protocol Number: ADU-CL-16  
Version and Date: Version 1.0, 18JUL2019

- contains information to indicate that the event ended before the treatment start date, then set the AE start day to the 1st day of the month of the AE start date.
- Otherwise, set the AE start date to the treatment start date.
- AE end dates will not be imputed.

These imputation rules will also be applied to concomitant medication dates.

### **Treatment and Study End Date**

Missing treatment and study end dates will not be imputed at the end of the study.

### **Date of Initial Multiple Myeloma Diagnosis**

- If the date is completely missing, no imputation will be conducted.
- If the date is missing month and day, they will be set to 01 January.
- If the date is missing only day, it will be set to 01 of the month.

## **5.7. Multiple Assessments and Visit Windows**

Nominal visits (e.g. those identified by the study CRF) will be the basis of summarization and statistical analysis; no visit date windowing will be conducted. Unscheduled data may be included in summaries of most extreme and baseline; summaries of specific abnormalities any time post-baseline; and subject data listings.

## **5.8. Missing Data**

Missing data imputation for AE, concomitant medication, and date of diagnosis date imputations are described in Section 5.6. Otherwise, missing data will not be imputed.

# **6. STUDY SUBJECT DATA**

## **6.1. Analysis Populations/Sets**

The Safety population (SAF) is defined as all subjects who receive any amount of study drug. All reporting of study data will be based on this population.

Additional analysis populations are described in the study protocol; however, the SAF is the only analysis set used for reporting study data in this ASAP, unless otherwise specified.

## **6.2. Subject Disposition**

Sponsor: Aduro Biotech, Inc.  
Protocol Number: ADU-CL-16  
Version and Date: Version 1.0, 18JUL2019

Summaries of analysis population membership; final study status (ongoing, completed or discontinued), including reasons for study discontinuation; treatment status (ongoing, completed or discontinued), including reasons for treatment discontinuation will be produced based on all subjects enrolled in the study. Time on study and duration of treatment will also be summarized.

Screen failures and final subject disposition status will be listed.

### 6.3. Protocol Deviations

Protocol deviations will be identified and classified as major or minor (violations) before the database is locked. Major protocol deviations may include but are not limited to:

- Violation of Inclusion/Exclusion Criteria
- Dose not properly administered
- Use of prohibited therapies

Protocol deviations will be summarized by cohort.

A listing of protocol deviations will be provided.

### 6.4. Demographic and Baseline Characteristics

Subject demographics will be summarized and listed for the SAF. These will include age in years, sex, ethnicity, race, baseline height (cm), baseline weight (kg), and baseline BMI (kg/m^2). Age will also be categorized as a categorical variable (< 65, ≥ 65) for reporting.

The following conversions and equations will be used as applicable:

- Height (in cm) = height (in inches) \* 2.54
- Weight (in kg) = weight (in lbs) \* 0.4536
- BMI (kg/m^2) = weight(kg)/[height(m)]

Baseline disease characteristics will also be summarized by cohort. Subject's Eastern cooperative oncology group (ECOG) performance status, duration of time from initial diagnosis to informed consent (in months); International staging system (ISS) stage at diagnosis and study entry; Revised ISS (R-ISS) stage at diagnosis and study entry; MM heavy chain subtype at diagnosis; MM light chain subtype at diagnosis and study entry; cytogenetics abnormalities at diagnosis; evidence of lytic bone disease at study entry; evidence of extramedullary disease at diagnosis and study entry; and any prior cancer treatments categories (Yes/No) collected on the eCRF will be displayed.

Subject demographics and baseline characteristics will be listed.

## 6.5. Medical History

General medical history data will be listed.

## 6.6. Prior and Concomitant Medication

Concomitant medications will be coded to anatomical therapeutic chemical (ATC) class and preferred name based on the WHO Drug Dictionary (WHO-DDE B2, September 2017). Prior medications are those which have been identified to have been discontinued prior to first study treatment (e.g. taken exclusively during the pre-therapy period). Concomitant medications are those which have been identified to have been taken at any point during the on-therapy period.

Prior and concomitant medications will be presented in data listings; medications which do not occur during the on-therapy period will be identified.

## 6.7. Prior Anticancer Therapies

Prior anticancer therapies are collected in the eCRF and data will be presented in data listings:

- Prior radiotherapy including the site of radiotherapy and reason for therapy
- Prior cancer related surgery including type of surgery and reason for surgery
- Prior cancer systemic therapy including line of therapy, transplant information (if applicable), number of cycles and best overall response. Also, minimal residual disease (MRD) status, relapse or progression, reason for therapy and reason medication was stopped. Each therapy will be coded to ATC class and preferred name based on the WHODD (September 2017)
- Transfusions including type, number of units and indication for transfusion

## 6.8. Study Drug Exposure and Compliance

Data will be summarized for BION-1301 study treatment and will be displayed by each Phase 1 cohort.

Duration of treatment (in months, as described in Section 5.3) will be summarized as a continuous variable for BION-1301.

The number of infusions of BION-1301 will be reported as both a continuous and categorical outcome; categories for reporting will be < 5 infusions; 5 to 10 infusions; > 10 to 15 infusions; and > 15 infusions.

Sponsor: Aduro Biotech, Inc.  
Protocol Number: ADU-CL-16  
Version and Date: Version 1.0, 18JUL2019

The number of cycles of administration of BION-1301 will be reported as a continuous and categorical outcome; categories for reporting will include: < 5 Cycles; 5 to 15 Cycles; > 15 to 25 Cycles; and > 25 Cycles.

The average volume administered for each infusion within a cycle will be summarized. Total infusion volume administered at each infusion is collected on the eCRF. The average for each subject will be calculated as:

$$\frac{\sum(\text{total volume administered at each infusion})}{\text{number of infusions within the cycle}}$$

The average dose for each BION-1301 cycle will be summarized. Total expected dose of BION-1301 is reported at each infusion and is collected on the eCRF. As interruptions can occur, the total of dose given will be calculated as:

$$\frac{\text{Volume administered}}{\text{Volume Prepared}} \times \text{Total Dose}$$

The average dose within a cycle for each subject will be calculated as:

$$\frac{\sum(\text{total dose received at each infusion})}{\text{number of infusions within the cycle}}$$

The incidence of infusion interruptions as well as the total number of interruptions will be displayed. Reasons for infusion interruptions will be summarized. Also, subjects who discontinued BION-1301 infusion prior to completion along with the reason will be summarized.

BION-1301 administration, infusion interruption, as well as any derived drug exposure metrics, will be listed.

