## 5.2. Reference Dates

- Informed Consent date is defined as the eCRF provided date on which a subject signed the informed consent.
- Treatment start date is defined as the date of first dose of study drug.
- Treatment end date is defined as the date of last dose of study drug.
- Age will not be calculated and will come directly from the eCRF. The eCRF uses the informed consent date as its reference date for age calculation.
- Safety data, such as AEs and laboratory assessments will use the treatment start date as a reference date.
- Study day will be based on treatment start date as a reference date.

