### 9.1. Adverse Events

After signing informed consent, and prior to the first study drug administration, any medical occurrence considered related to screening procedures (e.g. tumor biopsy, venipuncture) will be captured as an AE; all other medical events will be captured in the subject's medical history.

AEs will be assessed for severity using the NCI-CTCAE v. 4.03, relationship to BION-1301 (Definitely Related, Probably Related, Possibly Related, Unlikely Related, Unrelated), and seriousness (Yes, No). AEs will be considered treatment-emergent if the event occurs within the on-therapy period, the event was pre-existing and worsened in severity or became serious after the initiation of study drug.

An overview of treatment-emergent AEs (TEAEs) will be produced displaying counts and percentages of subjects with any incidences of: TEAEs, TEAEs with CTCAE Grade 3 or higher, TEAEs related to study treatment, TEAEs with CTCAE Grade 3 or higher related to study treatment, SAEs, TEAEs leading to study drug discontinuation, infusion-related reactions (IRRs), TEAEs leading to BION-1301 dose reduction/interruption; dose-limiting toxicities (DLTs), TEAEs of special interest (AESIs), and fatal TEAEs.

A separate overview of AEs identified as IRRs related to BION-1301 will be provided. This display will include the number of infusions received by subjects, the number of subjects having an IRR, total number of IRRs per subject, maximum IRR grade, and dose modifications resulting from IRRs.

Sponsor: Aduro Biotech, Inc.  
Protocol Number: ADU-CL-16  
Version and Date: Version 1.0, 18JUL2019

Adverse events will be coded based on the Medical Dictionary for Regulatory Affairs (MedDRA, Version 20.1) for reporting by system organ class (SOC) and preferred term (PT) in descending order of overall incidence. Events will be summarized. For these summaries, subjects with multiple AEs with the same SOC and/or PT will only be counted once at each level of summarization.

Summaries of adverse events by SOC and PT will include the following types:

- TEAEs;
- TEAEs related to study treatment (Definitely Related, Probably Related, or Possibly Related);
- TEAEs with CTCAE Grade 3 or higher;
- TEAEs with CTCAE Grade 3 or higher related to study treatment;
- BION-1301 IRR;
- TEAEs leading to dose reduction/interruption;
- SAEs;
- TEAEs leading to study drug discontinuation.

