To account for potential differences in the extent of exposure between the treatment categories, a subject-year adjusted rate will also be presented. The rate is calculated as the number of subjects with an event divided by the total subject-years of safety observation, where subject-years of safety observation for each subject is defined as duration of safety observation in days divided by 365.25.

A comprehensive listing of all AEs reported will be provided in a by-subject data listing. Furthermore, a separate listing of SAEs will be provided.

Events occurring during the pre-therapy study period will be listed.

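### Does the SAP's average dose per cycle hide how much BION-1301 subjects received?

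*SAP*

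**What the plan says.** Section 6.8 of the SAP (Study Drug Exposure and Compliance) sets out the exposure tables, displayed by Phase 1 cohort. The dose row is introduced with "The average dose for each BION-1301 cycle will be summarized". The derivation follows a few lines later under "The average dose within a cycle for each subject will be calculated as", and the formula divides the summed dose received by the "number of infusions within the cycle". Dose received at one infusion is the expected dose multiplied by volume administered over volume prepared. The volume row just before it has the same denominator and a clearer description: "The average volume administered for each infusion within a cycle will be summarized".

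The same section summarises treatment duration, the numbers of infusions and cycles over the whole of treatment, infusion interruptions with reasons, and infusions stopped early. It lists administration records and derived exposure measures by subject. It specifies no total mg per cycle, no cumulative mg and no received-to-planned ratio. Duration stops at the final dose (Section 5.2): "Treatment end date is defined as the date of last dose of study drug". The exposure adjustment of adverse event rates in Section 9.1 is by time: "To account for potential differences in the extent of exposure between the treatment categories, a subject-year adjusted rate will also be presented".

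**The concern.** Three things catch the eye.

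- The introductory sentence can be read as promising the dose per cycle, while the formula returns the dose per infusion. A reader who trusts the label would take the weekly cohort 6 to have received the same amount per cycle as cohort 4.
- The denominator is not expressly stated to be infusions given rather than infusions scheduled.
- The section heading includes compliance, and Protocol 7.4.8 sets a target of full compliance, yet no quantity compares dose received with dose planned.

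The primary objective is safety and tolerability. Protocol 7.4.5 and 7.4.5.1 foresee held doses and a change from weekly to two-weekly dosing. If the exposure tables could not show such shortfalls, a cohort might appear to have tolerated more drug than it received.

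**Working it through.** There is no figure in the plan to reproduce, so the formula is applied to the SAP's own cohorts.

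**Inputs.** SAP Table 1: cohort 4 is 1350 mg Q2W, cohort 5 is 2700 mg Q2W, cohort 6 is 1350 mg weekly for eight doses and then Q2W. SAP Table 2: two infusions per cycle on Q2W; four in each of Cycles 1 and 2 on the weekly schedule.

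**Formula.** Metric = (sum of mg received in the cycle) / (infusions in the cycle).

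**Full dosing, Cycles 1 and 2.**

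| Cohort | Cycle total (mg) | Metric (mg) |
|---|---|---|
| 4 | 2 × 1350 = 2700 | 2700 / 2 = 1350 |
| 5 | 2 × 2700 = 5400 | 5400 / 2 = 2700 |
| 6 | 4 × 1350 = 5400 | 5400 / 4 = 1350 |

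Cohort 6 receives twice cohort 4's cycle total and the same as cohort 5's, and the metric shows neither. From Cycle 3 cohort 6 is also on two infusions per cycle, so the difference in infusion frequency ends.

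**Partial and omitted infusions (hypothetical subjects, 1350 mg level).**

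- Weekly, three full infusions and one half: 4725 / 4 = 1181.25 mg, and 4725 / 5400 = 87.5% of plan. The metric falls in step, since 1181.25 / 1350 = 87.5%.
- Weekly, three of four given: 4050 / 3 = 1350 mg, and 4050 / 5400 = 75% of plan. The metric does not move.
- Q2W, one of two given: 1350 / 1 = 1350 mg, and 1350 / 2700 = 50% of plan. The metric does not move.

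**Which denominator?** With scheduled infusions below the line, the last case would be 1350 / 2 = 675 mg, so the choice would matter. But the numerator sums doses received, the volume row averages what was administered, and an infusion that never took place has no prepared or administered volume. Section 9.1 also counts infusions as received: "This display will include the number of infusions received by subjects". Nothing in the SAP points to scheduled infusions.

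**Can omissions be seen elsewhere?**

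- *Mid-course gap.* A Q2W subject with last dose on Day 155 was due (155 − 1)/14 + 1 = 12 infusions. Ten infusions against a duration of 155/30.4375 = 5.1 months gives 10/12 = 83%. The inputs are duration and infusion count, both planned.
- *Hold just before stopping.* Suppose a Q2W subject is dosed on Days 1, 15 and 29, is held on Day 43 and stops on Day 50. Duration is 29 − 1 + 1 = 29 days, with three infusions and a metric of 4050 / 3 = 1350 mg, although 4050 / 5400 = 75% of plan to discontinuation was received. These three rows miss the hold. But Day 43 is Cycle 2 Day 15, and Protocol 7.4.5 allows logistical interruptions only after four cycles. A hold that early would ordinarily be for tolerability and would appear in the Section 9.1 table of adverse events that led to a dose cut or interruption. Otherwise it may be a deviation, summarised by cohort under Section 6.3.
- *Cycle 1.* Under Protocol 7.1.1.1 a subject who misses a scheduled Cycle 1 dose without a DLT is not evaluable for escalation, so the row could not have misled a dose decision.

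**The case for a change.** The case for a change is that amount received against amount assigned is basic to describing tolerability, and the remedy looks cheap. The cycle total is the numerator already computed, it could follow the CRF cycle labels because Section 5.7 says "Nominal visits (e.g. those identified by the study CRF) will be the basis of summarization and statistical analysis", and cumulative mg is its sum. The existing tables also leave some holes. Interruption summaries describe only infusions that were started. Infusion counts are for the whole of treatment, not per cycle. A permitted logistical hold after Cycle 4, followed directly by discontinuation, need not appear as an adverse event or a deviation and would lower neither duration nor infusion count.

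All of that is true, and it supports calling cycle totals a useful optional row. It does not show a defect. The protocol promises no dose-intensity analysis. Administration is listed by subject, and with 21 subjects totals can be added up from the listings. The tables and listings are itemised in a separate document that is not available here, so absence from the final output cannot be confirmed. A received-to-planned ratio is not so cheap. It needs a planned dose for each subject, including the cohort 6 level from Cycle 3, which SAP Table 2 allows to differ from the weekly level. It also needs a discontinuation date distinct from the last dose, which the documents do not say is collected. And it would mix holds for toxicity with the logistical interruptions that the protocol permits, which weakens it as a measure of tolerability.

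**Conclusion.** No change to the plan is needed. The label is loose, but the formula beneath it is unambiguous about the division, and an analyst will take the denominator as infusions given. A mean per infusion is meant to be 1350 mg for both cohorts 4 and 6. The two-fold difference in their Cycle 1 and 2 totals comes from the schedule, which the cohort label states. The extra dose summaries would be additions to a descriptive table, not corrections of a wrong one.

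The consequence is small. Protocol 7.6 disclaims any comparison of dose cohorts, SAP Section 4 performs no significance tests, and Section 3.6 records that development stopped after cohort 6 completed treatment. No estimate, escalation decision or safety conclusion turns on this row. A clearer row title can be settled when the tables are laid out.

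This conclusion assumes that the planned dose per infusion equals the cohort dose in Cycles 1 and 2, that infusions not given carry no administration record, and that the listings contain the infusion-level doses that Section 6.8 describes. The missed-dose patterns are illustrations, not trial data.

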## 7. EFFICACY

Efficacy assessments evaluated in Phase 1 will be included in subject listings and will be presented on the SAF.

### 7.1. Tumor Response Assessments

Tumor assessment were performed throughout the study and evaluated according to the International Myeloma Working Group (IMWG) criteria. Response data as assessed by the investigator will be listed.

Sponsor: Aduro Biotech, Inc.  
Protocol Number: ADU-CL-16  
Version and Date: Version 1.0, 18JUL2019

## 7.2. Urine and Serum M-Protein

Efficacy laboratory assessments were collected throughout the study. Change from baseline and percent change from baseline will be derived as applicable and displayed in subject listings. The maximum percent reduction from baseline will be summarized by cohort.

## 8. PHARMACOKINETICS/PHARMACODYNAMICS

PK parameters will be assessed by non-compartmental analysis by a separate vendor, and will be discussed in a separate PK/PD/biomarker Analysis Plan.

## 9. SAFETY

All safety analysis reporting (tables and listings) will be based on the SAF. Summary tables will be presented by cohort and overall. Safety data will be listed by cohort, subject, cycle and infusion as applicable.

### 9.1. Adverse Events

After signing informed consent, and prior to the first study drug administration, any medical occurrence considered related to screening procedures (e.g. tumor biopsy, venipuncture) will be captured as an AE; all other medical events will be captured in the subject's medical history.

AEs will be assessed for severity using the NCI-CTCAE v. 4.03, relationship to BION-1301 (Definitely Related, Probably Related, Possibly Related, Unlikely Related, Unrelated), and seriousness (Yes, No). AEs will be considered treatment-emergent if the event occurs within the on-therapy period, the event was pre-existing and worsened in severity or became serious after the initiation of study drug.

An overview of treatment-emergent AEs (TEAEs) will be produced displaying counts and percentages of subjects with any incidences of: TEAEs, TEAEs with CTCAE Grade 3 or higher, TEAEs related to study treatment, TEAEs with CTCAE Grade 3 or higher related to study treatment, SAEs, TEAEs leading to study drug discontinuation, infusion-related reactions (IRRs), TEAEs leading to BION-1301 dose reduction/interruption; dose-limiting toxicities (DLTs), TEAEs of special interest (AESIs), and fatal TEAEs.

A separate overview of AEs identified as IRRs related to BION-1301 will be provided. This display will include the number of infusions received by subjects, the number of subjects having an IRR, total number of IRRs per subject, maximum IRR grade, and dose modifications resulting from IRRs.

Sponsor: Aduro Biotech, Inc.  
Protocol Number: ADU-CL-16  
Version and Date: Version 1.0, 18JUL2019

Adverse events will be coded based on the Medical Dictionary for Regulatory Affairs (MedDRA, Version 20.1) for reporting by system organ class (SOC) and preferred term (PT) in descending order of overall incidence. Events will be summarized. For these summaries, subjects with multiple AEs with the same SOC and/or PT will only be counted once at each level of summarization.

Summaries of adverse events by SOC and PT will include the following types:

- TEAEs;
- TEAEs related to study treatment (Definitely Related, Probably Related, or Possibly Related);
- TEAEs with CTCAE Grade 3 or higher;
- TEAEs with CTCAE Grade 3 or higher related to study treatment;
- BION-1301 IRR;
- TEAEs leading to dose reduction/interruption;
- SAEs;
- TEAEs leading to study drug discontinuation.

To account for potential differences in the extent of exposure between the treatment categories, a subject-year adjusted rate will also be presented. The rate is calculated as the number of subjects with an event divided by the total subject-years of safety observation, where subject-years of safety observation for each subject is defined as duration of safety observation in days divided by 365.25.

A comprehensive listing of all AEs reported will be provided in a by-subject data listing. Furthermore, a separate listing of SAEs will be provided.

Events occurring during the pre-therapy study period will be listed.

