7.1.1.1.1 Dose-limiting Toxicity Criteria

During Phase 1, the DLT evaluation period is defined as the first 28 days of treatment (Cycle 1). The occurrence of any of the toxicities presented in Table 7-2 will be considered a DLT unless clearly and incontrovertibly due to disease progression or extraneous causes. DLTs should be assessed and reported as directed in [Section 8](#).

Table 7-2. Criteria for Defining Dose-limiting Toxicities

Grade 5 event not clearly due to disease progression or extraneous causes
Hematologic toxicity defined as: 
 • Febrile neutropenia of any duration • Grade 4 neutropenia or thrombocytopenia that persists for >7 days, or Grade 3 thrombocytopenia associated with bleeding
Serum chemistry values consistent with Hy's Law criteria (all 3 of the following must co-exist): 
 • Alanine aminotransferase or aspartate aminotransferase $\geq 3\times$ institutional upper limit of normal (ULN) • Total bilirubin $\geq 2\times$ ULN • Alkaline phosphatase $< 2\times$ ULN
Grade 3 or higher infusion-related reaction per NCI CTCAE v 4.03
Any other Grade 3 or higher non-hematologic toxicity except: 
 • Grade 3 nausea, vomiting, or diarrhea that persists <72 hours with adequate antiemetic and other supportive care • Grade 3 fatigue <7 days

Emergent safety data will continue to be evaluated on an ongoing basis by the SRT.

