7.5.3.7 Clinical Laboratory Evaluation for Safety

Routine hematology, serum chemistry, and urinalysis will be performed throughout the study as a safety measure (Section 7.5.4.2). The Medical Monitor may, depending on study criteria, be consulted before enrollment about a potential subject with abnormal laboratory values that are not considered clinically significant by the Investigator.

The clinical significance of laboratory parameter findings will be determined by the Investigator throughout the study. All abnormal laboratory values considered clinically significant by the Investigator must be recorded in the AE page of the eCRF. Any abnormal test that is determined to be an error does not require reporting as an AE. Clinically significant abnormal laboratory values occurring during the clinical study will be followed until repeat tests return to normal, stabilize, or are no longer clinically significant.

Additional safety laboratory assessments include immunogenicity (antidrug antibodies; ADA; neutralization assays (Section 7.5.4.2.1)).

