8.1.3 Events of Special Interest

Drug induced liver injury is considered an event of special interest in this study and is defined as serum chemistry laboratory values consistent with Hy's Law criteria (i.e. all 3 of the following must coexist):

- $ALT \text{ or } AST \geq 3 \times ULN$
- $Total \text{ bilirubin} \geq 2 \times ULN$
- $ALP < 2 \times ULN$

Laboratory values meeting all criteria for potential Hy's Law cases from the time of first study drug administration through the EOT visit should be reported following SAE reporting procedures [Section 8.3](#).

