## **9.2. Clinical Laboratory Evaluations**

Clinical chemistry and hematology parameters will be reported based on the International System of Units (SI). The following laboratory evaluations will be reported in data summaries, with asterisks (\*) indicating those that will be graded using NCI-CTCAE:

Hematology: Hematocrit, white blood cell\*, absolute neutrophil count\*, lymphocytes\*, hemoglobin\*, monocytes, eosinophils, basophils, red blood cell, and platelet count\*

Clinical chemistry: sodium\*, potassium\*, chloride, bicarbonate, glucose\*, blood urea nitrogen, creatinine\*, lactate dehydrogenase, alanine aminotransferase\*, aspartate aminotransferase\*,

Sponsor: Aduro Biotech, Inc.  
Protocol Number: ADU-CL-16  
Version and Date: Version 1.0, 18JUL2019

alkaline phosphatase\*, bilirubin (total\*, direct, indirect), total protein, albumin\*, calcium, magnesium\*, phosphate\*, and uric acid.

Safety laboratory assessments will be summarized by absolute value and change from baseline at each visit will be displayed by cohort and cycle.

Shift tables displaying the shift from baseline to the worst value of NCI-CTCAE grade will be presented based on the most extreme change as it relates to the relevant NCI-CTCAE definition.

All laboratory parameters will be provided in subject data listings.

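### The only event of special interest, liver injury, is defined by coexisting laboratory values, but the SAP counts it only from site-reported events and never from the laboratory data

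*SAP*

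**What the plan says.** **Definition.** Protocol 8.1.3: "Drug induced liver injury is considered an event of special interest in this study and is defined as serum chemistry laboratory values" meeting Hy's Law criteria, where "all 3 of the following must coexist": ALT or AST at least 3 times ULN, total bilirubin at least 2 times ULN, and ALP below 2 times ULN. No symptom, diagnosis or causality judgement is part of it. Table 7-2 lists the same triad as a DLT.

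**Reporting by sites.** Protocol 8.1.3 asks that potential Hy's Law "cases from the time of first study drug administration through the EOT visit should be reported following SAE reporting procedures". Section 8.3.1 sets 24 hours for SAE information. For DLTs, Section 7.1.1.1.1 says "DLTs should be assessed and reported as directed in" Section 8.

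**Counting.** SAP 9.1 plans an overview of treatment-emergent events whose last rows are "TEAEs of special interest (AESIs), and fatal TEAEs". Events of special interest are not among its summaries by system organ class and preferred term, and the SAP does not restate the triad or derive it.

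**Laboratory outputs.** SAP 9.2 gives each analyte by visit, as value and change from baseline. It adds: "Shift tables displaying the shift from baseline to the worst value of NCI-CTCAE grade will be presented". All laboratory results are also listed by subject. No table, flag or listing of subjects who meet the combined criteria is specified.

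**The concern.** The event is a numerical condition on four tests that the trial already collects, yet the planned count never looks at those tests. It depends on a site noticing the combination and reporting it. Failure to report can only lower the count, so a zero in the overview would mean that no case was reported. A reader of the report is likely to take it to mean that no subject met the criteria.

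DLTs and treatment-emergent events form the primary endpoint in SAP Section 2, and the same triad feeds both. The laboratory tables cannot serve as a check, because they show each analyte separately and the definition is about their coincidence.

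**Working it through.** The documents state no figure for this event, so there is none to reproduce. The check traces the event from its definition to each planned output, then illustrates the size.

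**1. Where an unreported case would appear**

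| Planned output (SAP) | Source | Shows an unreported case? |
|---|---|---|
| AESI row of the overview, 9.1 | Reported treatment-emergent events | No |
| DLT row of the overview, 9.1 | DLTs assessed and reported by sites | No |
| SAE row, SAE summary and SAE listing, 9.1 | Reported SAEs | No |
| Analyte summaries by visit, 9.2 | Laboratory data, nominal visits (5.7) | Not as a combination |
| Shift to worst grade, 9.2 | Laboratory data, each analyte separately | Not as a combination |
| Laboratory listings, 9.2 | Laboratory data by subject | Visible, but not flagged or counted |

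**2. Why separate tables cannot give the joint count.** If k of N subjects have raised ALT or AST and m of N have raised bilirubin, the number with both lies between max(0, k + m − N) and min(k, m). With N = 21 (SAP 3.1):

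- k = 2, m = 2: from max(0, −17) = 0 to 2.
- k = 4, m = 3: from max(0, −14) = 0 to 3.

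The worst-grade shift tables also take each analyte at its own worst time, so even a subject who is high on both need not have been high on both together.

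**3. Windows.** SAP 5.4.1 treats the event of special interest as treatment-emergent up to the EOT visit. Table 2-1, footnote 3, allows that visit up to 28 + 7 = 35 days after the last dose. SAP 5.4 ends the on-therapy period 28 days after the last dose, and SAP 9.1 uses that period to define a treatment-emergent event. A new case on days 29 to 35 is thus reportable under 5.4.1 but outside the on-therapy limb of 9.1. Whether it enters the AESI row depends on which section the programmer follows.

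**4. Size, as an illustration only.** This assumes that all 21 enrolled subjects were treated. Limits are exact Clopper-Pearson; for zero events the upper limit is 1 − 0.025^(1/21) = 16.1%.

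| Subjects counted | Percentage | 95% CI |
|---|---|---|
| 0/21 | 0% | 0 to 16.1% |
| 1/21 | 4.8% | 0.1 to 23.8% |
| 2/21 | 9.5% | 1.2 to 30.4% |

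Within a cohort, one case is 1/3 = 33.3% or 1/6 = 16.7%. The documents do not give the cohort sizes. If each of the six cohorts had at least 3 subjects, that accounts for 6 × 3 = 18 of the 21, and at most one cohort can have reached 6.

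**The case against.** The strongest reply is that ascertainment is better protected than the SAP suggests. A reader might infer that the event rests on voluntary recognition, because Protocol 7.5.3.7 says "All abnormal laboratory values considered clinically significant by the Investigator must be recorded in the AE page of the eCRF". That is the general rule for laboratory abnormalities. Section 8.1.3 has a specific rule for this triad with no clinical-significance filter, and it uses the SAE route. Monitoring, data validation (Protocol 9.3 and 10.5) and Safety Review Team oversight (SAP 3.4) add further chances to catch a case. This stands: the gap opens only when a site fails to follow a reporting rule and later checks miss it. None of those checks, however, is described as a Hy's Law screen.

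A second reply is that the data remain visible. Laboratory values are listed for 21 subjects, SAP 5.7 mentions summaries of specific abnormalities, and SAP Section 12 puts the list of outputs in a separate document. So a case is not hidden, and a combined table elsewhere cannot be excluded. The SAP text still specifies none.

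A third reply is that a program cannot settle the count alone, and this also stands. Table 7-2 sits under an exception for toxicity clearly due to progression or extraneous causes, which laboratory values cannot resolve. Section 8.1.3 gives no time window for coexistence. Inclusion criterion 6 admits AST or ALT up to 3 times ULN, and bilirubin up to 3 times ULN in Gilbert's disease, so a subject could be at or near the thresholds before dosing. A programmed hit is a candidate, not a confirmed DLT.

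**Conclusion.** The point holds in a limited form. No count specified in the SAP text applies the protocol's own definition of its only event of special interest. A case that a site did not report would appear in the laboratory listings and nowhere in the counts. The windows in SAP 5.4 and 5.4.1 also disagree for days 29 to 35 after the last dose.

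The effect is confined to the accuracy of the final safety report. The difference between 0/21 and 1/21 (4.8%) is hypothetical; the documents show no missed case. A reader might infer that dose-escalation decisions were compromised. The documents do not support that: they show no missed DLT, the study was terminated after Phase 1, Phase 2 was not enrolled, and the SAP omits the RP2D analyses and plans no significance tests.

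This reading assumes that the separate list of outputs contains no combined liver-test table. If it does, the remaining step is to name that table in the SAP and resolve the windows.

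**What to change.** In SAP 9.1 and 9.2:

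- Derive the three criteria of Protocol 8.1.3 by program from all scheduled and unscheduled chemistry, from first dose to the EOT visit.
- State the coexistence window, for example the same sample, and show baseline values so that subjects near the thresholds at entry can be identified.
- Tabulate, by cohort and overall, the number of subjects who meet all three criteria, and list their full liver-test profiles.
- Flag first occurrences in Days 1 to 28 as candidate DLTs, subject to the attribution clause that governs Table 7-2.
- Reconcile the derived list with reported AESIs, SAEs and DLTs before database lock, and query discrepancies.
- Reconcile SAP 5.4, 5.4.1 and 9.1 so that one window governs the AESI row.

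The tests are already collected, and the change applies the protocol's criteria without altering a clinical rule. For 21 subjects it costs a short program, one table and one listing, with possibly a few false flags and site queries. A zero in the report would then have been checked against the laboratory data.
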